## **7.2 Medical History**

Medical history data will be summarized and presented using body systems and conditions/diagnoses as captured on the eCRF. The body systems will be presented in alphabetical order and the conditions/diagnoses will be presented in alphabetical order within each body system. The number and percentage of subjects with a particular condition/diagnosis will be summarized. Subjects reporting more than one condition/diagnosis within a body system will be counted only once for that body system.

## **7.3 Previous Treatment and Concomitant Medications**

Prior and concomitant medications will be summarized. A prior medication is defined as any medication taken prior to the date of the first dose of study drug. A concomitant medication is defined as any medication that started prior to the date of the first dose of study drug and continued to be taken after the first dose of study drug or any medication

---

that started on or after the date of the first dose of study drug, but not after the date of the last (maximum) dose of study drug. The number and percentage of subjects taking prior or concomitant medications will be summarized by generic drug name based on the WHO Drug Dictionary. Note that prior HCV medications (IFN and RBV) will be summarized separately from other prior medications.

Medications for the treatment of HCV taken in the PT Period will be collected and will be summarized by generic drug name. A post-treatment medication for the treatment of HCV is defined as any medication taken on or after the last dose of study drug and entered as "Post treatment HCV medications" on the eCRF.

## **8.0                   Patient Disposition**

All patient disposition summaries will be performed in the safety population using the safety population table format. The number of subjects for each of the following categories will be summarized.

- Enrolled Subjects;
- Subjects who took at least one dose of study drug;
- Subjects who completed study drug;
- Subjects who discontinued from study drug;
- Subjects who completed the study;
- Subjects who prematurely discontinued from the study.
- Subjects ongoing in the Post-Treatment Period (if applicable at the time of the interim analysis);

The number and percentage of subjects who discontinued study drug will be summarized by reason (all reasons) and by primary reason (per eCRF). Similar summaries will be provided for discontinuations from the study.

The number and percentage of subjects will be summarized for:

- Subjects with interruptions of all study drugs for toxicity management;

- Subjects with any RBV dose modification;
  - Subjects with RBV dose modification due to decrease in hemoglobin;
  - Subjects with RBV dose modification due to decrease in creatinine clearance;
  - Subjects with RBV dose modification due to weight change;
  - Subjects with RBV dose modification due to other reasons;
- Subjects with any RBV dose modification to 0 mg (i.e., RBV interruptions).

Reasons for study drug interruption and RBV dose modifications will be presented in the CSR listings.

The number and percentage of screened subjects who screen failed will be calculated, and the reasons for screen failure (inclusion/exclusion criteria, withdrew consent, lost to follow-up, and/or other) will be summarized. A listing of reasons for screen failure will be provided for all subjects who screen failed.

## **9.0 Study Drug Exposure and Compliance**

Exposure and compliance will be summarized in the safety population using the safety population format.

### **9.1 Exposure**

Duration of exposure is defined for each subject as the last study drug dose date minus the first study drug dose date plus 1 day.

Descriptive statistics (n, mean, SD, median, minimum and maximum) will be presented. Study drug duration also will be summarized with frequencies and percentages using the following categories depending on the treatment duration:

- 12 weeks of treatment: 1 to 15 days, 16 to 30 days, 31 to 45 days, 46 to 60 days, 61 to 76 days, and > 76 days.
- 24 weeks of treatment: 1 to 15 days, 16 to 30 days, 31 to 60 days, 61 to 90 days, 91 to 120 days, 121 to 153 days, and > 153 days.

## **9.2                   Compliance**

For ombitasvir/paritaprevir/r tablet, dasabuvir tablet, and RBV tablet, tablet is the dose unit for drug accountability. For mini-tablets, bottle is the dose unit for drug accountability and the return status for each dose unit is recorded as either full/sealed, empty, or unsealed but not empty. A mini-tablet bottle is considered to be taken only if the return status is empty. For RBV solution, mL is the dose unit for drug accountability.

At each protocol-specified visit, the total number of dose units dispensed and returned is recorded for each type of study drug. The compliance for each type of dose unit within the Treatment Period will be calculated as the percentage of dose units taken or returned empty relative to the total number of dose units expected to be taken. The total number of dose units expected to be taken will be equal to the total number of dose units that should have been taken per the protocol for the duration that the subject was in the Treatment Period (date of last dose – date of first dose + 1 day). If a mini-tablet bottle is returned unsealed but not empty or if any dosing unit of study drug is not returned for reconciliation, then study drug compliance for that drug will not be calculated for that subject. Study drug interruptions due to an adverse event or other planned interruptions for toxicity management recorded on the eCRF will be subtracted from the duration. For compliance to RBV, RBV dose modifications due to adverse events, toxicity management, or weight changes as recorded on the RBV Dose Modifications eCRF will be used to modify the total number of unit that should have been taken. A subject is considered to be compliant if the percentage is between 80% and 120%. Compliance will be calculated for each subject and each type of dose unit and will be summarized with the N, mean, standard deviation, median, minimum, and maximum. In addition, the percentage of compliant subjects will be calculated for each study drug.

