### **5.5.6 Treatment Compliance**

The investigator or his/her designated and qualified representatives will administer/dispense study drug only to subjects enrolled in the study in accordance with the protocol. The study drug must not be used for reasons other than that described in the protocol.

All study drugs will be dispensed to subjects by study-site personnel under the direction of the investigator. At the start of the study, each subject along with their parent(s)/guardian(s) should receive counseling regarding the importance of dosing adherence with the treatment regimen with regard to virologic response and potential development of resistance. The start and stop dates of all study drugs will be recorded in the source documents and eCRFs. When dosing mini-tablets, the bottles should be checked thoroughly to ensure that no mini-tablets remained inside the bottle.

During the Treatment Period, subjects will be instructed to bring all study drug units (full, partial or empty) to the study site at each study visit. The study site personnel will inspect the contents of the study drug bottles and account for the returned study drug electronically at each Study Drug Accountability visit indicated in [Appendix C](#). If poor adherence is noted, the subject and parent(s)/guardian(s) should be counseled and this should be documented in the subject's source document.

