- s. Part 1: Study drugs will be dispensed every 2 weeks for subjects receiving the mini-tablets with study visit procedures occurring at Day 1, Weeks 2, 4, 6, 8 and 10. Subjects receiving the adult formulation will have drug dispensed at Study Day 1 and Weeks 4 and 8 for 12-week treatment.  
Part 2: Study drug dispensed every 4 weeks at regularly scheduled visits at Day 1 and Weeks 4 and 8 for 12-week treatment and Day 1 and Weeks 4, 8, 12, 16, and 20 for 24-week treatment. Drug accountability will be performed at each drug dispensation visit as outlined for mini-tablet, pellet and adult formulations.
- t. Study drugs are only dispensed at Week 12 for subjects who will receive 24 weeks of treatment.
- u. Dosing card is filled out with date and time (to the nearest minutes) of the 2 doses before PK draws in Part 1 and Part 2. Do not dispense the dosing card at Week 12 visit of Part 1 and at the Week 12 visit for subjects assigned to 12 weeks of treatment in Part 2 (Section 5.3.1.1).

- v. Only for Subjects taking RBV Solution
  - Part 1: Dispensed/Collected every 2 weeks for subjects receiving the mini-tablets with RBV with study visit procedures occurring at Day 1, Weeks 2, 4, and 8.
  - Part 2: Dispensed/Collected every 4 weeks at regularly scheduled visits at Day 1 and Weeks 4 and 8 for 12-week treatment and Day 1 and Weeks 4, 8, 12, 16, and 20 for 24-week treatment.
- w. In Part 1, intensive PK sampling will be done at Week 2 and sparse PK sampling at other visits (Section 5.3.2.1), while sparse PK sampling will be done at all PK visits in Part 2 (Section 5.3.2.1).
- x. The Subject will retain the subject number throughout the course of the study.
- y. Resistance sample will be collected at Day 1 and upon meeting virologic failure criteria.
- z. The Tanner Pubertal stage is assessed for subjects aged  $\geq 9$  to 17 years old. Tanner staging will not be repeated once the child reaches Tanner Stage 5.
- aa. The PRO should be administered as the first study procedure at each visit.
- bb. Subjects taking the mini-tablet/pellet formulations only.

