### 6.3 Missing Data Imputation

No data will be imputed for any efficacy or safety analyses except for analyses of the HCV RNA endpoints.

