## **10.5 Efficacy Subgroup Analysis**

The number and percentage of subjects with SVR12 across all subjects in the ITT population will be presented by the following subgroups:

- Age group ( $\geq 3 - 8$ ,  $\geq 9 - 11$ , and  $\geq 12 - 17$  years) and weight group (15 to 29 kg, 30 to 44 kg,  $\geq 45$  kg) at enrollment;

- HCV genotype and sub-genotype (1a, 1b, other 1, and 4);
- Prior HCV Treatment Experience (naïve, IFN-experienced)
- Prior IFN treatment response (among experienced) (prior non-responder, prior breakthrough, prior relapse, unknown, and interferon experienced-other);
- IL28B genotype (CC or non-CC), (CC, CT, or TT);
- Sex (male or female);
- Baseline fibrosis stage (F0-F1, F2, F3 or F4);
- Baseline HCV RNA level (< 800,000 IU/mL or  $\geq$  800,000 IU/mL; < median or  $\geq$  median);
- Race (Black versus non-black);
- Ethnicity (Hispanic/Latino versus none);
- Baseline height z-score (< -1, -1 to 1 or > 1);
- Drug compliance (< 80% versus  $\geq$  80%).
- Baseline creatinine clearance using the CC&G method for subjects at least 12 years old (< 50 mL/min,  $\geq$  50 mL/min);
- Baseline creatinine clearance using the Schwartz method for subjects from 3 to < 12 years old (< 60 mL/min/1.73 m^2,  $\geq$  60 mL/min/1.73 m^2)
- RBV dose modifications (yes/no).

The 2-sided 95% Wilson score confidence interval will be produced for each subgroup with at least 10 subjects.

In addition, stepwise logistic regression will be performed on virologic failure (on-treatment virologic failure or relapse) using subgroup variables as described above, if there are sufficient number of virologic failures. Some variables may be treated as continuous to decrease the chance of separation or quasi-separation and some variables may be eliminated if missing for too many subjects.

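### SAP 9.2 drops a child's compliance value for a mini-tablet drug because of one unresolved bottle, although the recorded bottle counts bound that value

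*SAP*

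**What the plan says.** SAP 9.2 makes the bottle the accountability unit for mini-tablets, with three possible return statuses: sealed, empty, or opened with something left inside. It then states: "A mini-tablet bottle is considered to be taken only if the return status is empty". Compliance is the number of units taken divided by the number expected over the treatment period. A few sentences later the same section sets a missing-value rule. Its trigger is: "If a mini-tablet bottle is returned unsealed but not empty or if any dosing unit of study drug is not returned for reconciliation". The consequence that the SAP attaches to this trigger is: "then study drug compliance for that drug will not be calculated for that subject".

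The value feeds two outputs in SAP 9.2, both per drug: a summary (N, mean, SD, median, range) and the percentage of compliant children. The definition for the latter is: "A subject is considered to be compliant if the percentage is between 80% and 120" percent. SAP 10.5 also lists an SVR12 subgroup beginning "Drug compliance (< 80% versus", whose other level is 80% or more. SAP 6.3 offers no fallback: "No data will be imputed for any efficacy or safety analyses", apart from the HCV RNA endpoints.

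**The concern.** The rule can be programmed, but it throws away information that sites already record. A partly emptied bottle leaves at most one dose in doubt, yet the remaining weeks of bottle counts for that drug are lost with it. The rule also overrides the SAP's own statement that only an empty bottle counts as taken, which already gives a partly emptied bottle the value zero.

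A partly emptied bottle is by definition an incomplete dose, so for this trigger the missing value is tied directly to dosing. Children whose doses went wrong in this way leave the summary, while children who returned whole bottles sealed stay in it.

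At stake are the per-drug compliance summary and the percentage compliant, reported by age group with about 12 mini-tablet children in each of the two younger groups (SAP 4.2, 5.1.2 and 9.0). The SAP 10.5 compliance subgroup is exposed too. Its loss cannot be counted, because SAP 10.5 does not say where a child without a value goes.

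**Working it through.** The plan gives no figure for this rule, so there is none to reproduce.

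**Inputs**
- Part 1 treatment lasts 12 weeks = 84 days (Protocol synopsis).
- Ombitasvir, paritaprevir and ritonavir are once daily, so N = 84 each. Dasabuvir is twice daily, so N = 168 (Protocol 5.5.1).
- Protocol 5.5.1 describes unit-dose packing. One bottle per drug per dose is my reading of that, and an assumption.
- Protocol Appendix C, note s: "Study drugs will be dispensed every 2 weeks for subjects receiving the mini-tablets". A two-week supply is 14 of 84 or 28 of 168 bottles.
- For the worked cases, bottles dispensed equal bottles expected (no replacement or spare supply).

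**Formula.** Let E be bottles returned empty, k unresolved (partly emptied or not returned) and m returned sealed. Each unresolved bottle contributes between 0 and 1 dose, so compliance lies between E/N and (E+k)/N, a width of k/N. In the worked cases E = N − k − m.

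| Case | Once daily, N = 84 | Dasabuvir, N = 168 |
|---|---|---|
| k = 1, rest empty | 83/84 = 98.8% to 100% | 167/168 = 99.4% to 100% |
| Two-week supply unreturned, rest empty | 70/84 = 83.3% to 100% | 140/168 = 83.3% to 100% |
| Largest k with lower bound at least 80%, rest empty | 16: 68/84 = 81.0% | 33: 135/168 = 80.4% |
| One bottle more | 17: 67/84 = 79.8% to 100% | 34: 134/168 = 79.8% to 100% |
| Sealed bottles plus one partly emptied, rest empty | 17 + 1: 66/84 = 78.6% to 67/84 = 79.8% | 34 + 1: 133/168 = 79.2% to 134/168 = 79.8% |

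The SAP sets every case in the table to missing. In the first three rows the child is certainly at 80% or more; in the last row, certainly below. Without the partly emptied bottle, a child with 17 of 84 sealed and 67 empty is calculated, at 67/84 = 79.8%. Leaving part of one more dose turns a known value below 80% into a missing one.

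**Size of the trigger.** From the strengths and doses in the Protocol synopsis, a dose is about 100/3.08 = 32.5 mini-tablets (dasabuvir, 15 to 29 kg) up to 150/1.0 = 150 (paritaprevir, 45 kg or more). One left behind is therefore 1/32.5 = 3.1% down to 1/150 = 0.7% of one dose.

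**Replacement supply.** Protocol 5.5.7 lets lost or damaged units be replaced through IRT. If 14 bottles are lost and replaced, a child may return 84 empty with 14 unresolved; the uncapped upper bound is 98/84 = 116.7%. With 17 it is 101/84 = 120.2%, outside the SAP's compliant range. The upper bound therefore needs a cap.

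**The case against.** Declining to calculate a percentage when intake is unknown is an explicit, prespecified convention. The affected outputs are descriptive, the summary reports N so lost values are visible, and bottle status stays on record. Exposure duration and PK samples at each Part 1 treatment visit give other evidence of intake. No hypothesis rests on compliance. All of this stands, and it keeps the point minor.

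Three limits on the remedy also stand. The bounds are tight only for a few bottles: an unreturned two-week supply is 14/84 = 16.7 points wide, and 17 of 84 bottles is 20.2 points. A shortfall made only of partly emptied bottles has an upper bound of 100%, so it is never classed below 80%, under the SAP or under the bounds. The non-return trigger also covers adult tablets and ribavirin, so changing it for mini-tablets alone leaves two conventions in one table.

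A reader might infer more than the documents support:
- *That many children lose their value.* No rate of residue or non-return is given. The Protocol 5.5.6 instruction that "the bottles should be checked thoroughly to ensure that no mini-tablets remained inside the bottle" is preventive and does not predict residue.
- *That reported compliance is biased in a known direction.* Sealed bottles stay in the calculation, so the direction is not fixed.
- *That all the missingness reflects poor adherence.* The link is direct for partly emptied bottles; for unreturned bottles it is plausible but not shown. Even a partly emptied bottle may hold only a trace of residue.

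**Conclusion.** The concern holds as a minor one. SAP 9.2 discards a value that the recorded counts bound, and nothing else in the documents softens the rule. With one unresolved bottle and all others empty, the discarded value is at least 98.8% (once daily) or 99.4% (dasabuvir). The class of 80% or more is settled for up to 16 of 84 or 33 of 168 unresolved bottles when the rest are empty.

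These figures assume a full 84-day course, one bottle per drug per dose, and dispensed supply equal to expected supply. More bottles per dose would narrow the one-bottle range. Spare or replacement bottles would change the worked figures, including the sealed-bottle cases, but not the lower bound E/N. The effect is confined to the compliance summary, the percentage compliant and the compliance subgroup, for about 24 mini-tablet children (SAP 4.2 allows up to 12 more). The primary ITT SVR12 result is unaffected.

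**What to change.** In SAP 9.2, for mini-tablets, replace the instruction not to calculate with two reported values:
- Lower bound: E/N, which follows the SAP's own rule that only an empty bottle counts as taken.
- Upper bound: (E+k)/N, with unresolved bottles credited only until the total reaches N, that is (E + min(k, max(0, N − E)))/N. Lost-and-replaced bottles are then not counted as extra doses.

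Report the number of children with any unresolved bottle. For each drug, classify as below 80% or as 80% or more when both bounds agree, and otherwise show *undetermined*. Carry that category into the SAP 10.5 compliance subgroup. State that a shortfall made only of partly emptied bottles will appear as 80% or more or as undetermined. Nothing is imputed, so SAP 6.3 is respected.

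The cost is SAP wording and a small programming change using statuses already collected. The downside is a slightly longer descriptive table, one extra subgroup row, and a non-return rule that differs from the one for tablets and ribavirin unless it is extended to them.

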## **10.0                   Efficacy Analysis**

### **10.1                   General Considerations**

All efficacy analyses will be performed in the ITT population, unless otherwise specified.

Missing data will be imputed as described in Section 6.3 for analyses of the HCV RNA endpoints of SVR.

Plasma HCV RNA levels will be determined for each sample collected by the central laboratory using the Roche COBAS® AmpliPrep/COBAS® TaqMan® HCV Quantitative Test, v2.0. The lower limit of detection (LLOD) and lower limit of quantification (LLOQ) for this assay (regardless of genotype) are both 15 IU/mL.

HCV RNA results that are detectable but not quantifiable are reported as "< 15 IU/ML HCV RNA DETECTED" and those that are undetectable are reported as "HCV RNA NOT DETECTED" in the database.

The notation "HCV RNA < LLOQ" is used to represent all HCV RNA values < 15 IU/mL, including values reported as "HCV RNA NOT DETECTED" or "< 15 IU/ML HCV RNA DETECTED." HCV RNA  $\geq$  LLOQ are all quantifiable values of 15 IU/mL or greater.

### **Definitions for HCV RNA Efficacy Endpoints**

A confirmed quantifiable value during treatment is defined as any two consecutive HCV RNA measurements  $\geq$  LLOQ (or 100 IU/mL for **Breakthrough**), either both during treatment or at the final treatment measurement and the next consecutive post-treatment measurement. A confirmed quantifiable post-treatment value is defined as any two consecutive post-treatment HCV RNA measurements  $\geq$  LLOQ.

A confirmed quantifiable value during treatment is defined as any two consecutive HCV RNA measurements  $\geq$  LLOQ (or 100 IU/mL for **Breakthrough**), either both during treatment or at the final treatment measurement and the next consecutive post-treatment measurement. A confirmed quantifiable post-treatment value is defined as any two consecutive post-treatment HCV RNA measurements  $\geq$  LLOQ.

**Breakthrough** = confirmed HCV RNA  $\geq$  100 IU/mL after HCV RNA < LLOQ during the Treatment Period; or confirmed increase from nadir in HCV RNA (two consecutive

---

HCV RNA measurements  $> 1 \log_{10}$  IU/mL above nadir) at any time point during the Treatment Period. A single breakthrough value ( $\geq 100$  IU/mL or  $> 1 \log_{10}$  above nadir) followed by lost to follow-up also will be considered a breakthrough (i.e., will not require confirmation).

**EOT failure** = HCV RNA  $\geq$  LLOQ at end of treatment with at least 6 weeks of treatment, where the HCV RNA value must be collected on or after Study Drug Day 36 and study drug duration  $\geq$  36 days.

**On-treatment virologic failure** = **Breakthrough** or **EOT failure**; if a subject meets both definitions of Breakthrough and EOT failure, he or she will be categorized as Breakthrough only.

**SVR4** = HCV RNA  $<$  LLOQ in the SVR4 window (4 weeks after the last actual dose of study drug) without any confirmed quantifiable ( $\geq$  LLOQ) post-treatment value before or during that SVR window.

**SVR12** = HCV RNA  $<$  LLOQ in the SVR12 window (12 weeks after the last actual dose of study drug) without any confirmed quantifiable ( $\geq$  LLOQ) post-treatment value before or during that SVR window.

**SVR24** = HCV RNA  $<$  LLOQ in the SVR24 window (24 weeks after the last actual dose of study drug) without any confirmed quantifiable ( $\geq$  LLOQ) post-treatment value before or during that SVR window.

**Relapse12** = confirmed HCV RNA  $\geq$  LLOQ between end of treatment and 12 weeks after last actual dose of study drug (up to and including the SVR12 window) for a subject with HCV RNA  $<$  LLOQ at Final Treatment Visit who completed treatment excluding reinfection as described below.

**Relapse24** = confirmed HCV RNA  $\geq$  LLOQ within the SVR24 window for a subject who achieved SVR12 and has HCV RNA data available in the SVR24 window, excluding reinfection.

---

**Relapseoverall** = confirmed HCV RNA  $\geq$  LLOQ between end of treatment and up to and including the last HCV RNA measurement collected in the PT Period for a subject with HCV RNA  $<$  LLOQ at Final Treatment Visit who completed treatment excluding reinfection.

